1. INTRODUCTION

Prostate cancer (PCa) is the second most common cancer in men, primarily affecting older men. The standard treatment for recurrent and metastatic Pca is ADT. It is also standard of care for men with intermediate or high risk localized prostate cancer who plan to get radiation to receive ADT in the neoadjuvant and adjuvant setting. It is well established that ADT causes muscle weakness and wasting, osteoporosis, and fatigue. Our preliminary data suggests that older men on ADT have significant physical performance deficits, functional impairments, and falls at higher rates than men in the general geriatrics population. HMB is a leucine metabolite which has been shown to decrease the rate of muscle protein breakdown. When given with arginine and lysine or glutamine, HMB has been shown to improve strength, fat-free mass and function in the general geriatrics population who are prone to sarcopenia. Use of HMB and/or amino acid supplementation in older men with PCa starting on ADT has not been reported. We will prospectively: 1) measure the change in body composition, strength, physical performance, and falls in older men with PCa starting on ADT, comparing those who receive HMB + AG versus those who do not, 2) evaluate the use of MRI and muscle biopsy to identify changes in muscle composition and muscle fatiguability that are known to occur in this patient population. We will test the hypothesis that HMB + AG can reduce the adverse change in body composition and strength/muscle fatiguability that occur when older men with PCa are started on ADT. With data obtained

in this study, a larger randomized study will be designed to compare interventions aimed at minimizing the adverse affects that occur with ADT initiation.

2. BACKGROUND

Seventy-five percent of Pca incidence and greater than 90% of Pca mortality occurs in men aged 65 years or older. PCa is the second most common cancer in American men, with more than 217,000 new cases anticipated in 2010. Men live with Pca for many years. Once patients develop biochemical recurrence (PSA rise) after prostatectomy for local disease, the median time to development of distant metastasis *in the absence of treatment* is 8 years and median time to death an additional 5 years after development of

ADT

Aging Low Testosterone Anemia

Inflammation Sarcopenia

(Lean) Weight Loss

Lowered Muscle Power

Weakness Impaired Mobility

Fatigue

metastases.³ Due to competing comorbidities, a significant number of older men with PCa will die with, not as a result of, their disease. In fact, only 39% of men diagnosed with PCa after age 67 die of their disease.⁴ Thus, it is extremely important for providers to be aware of potential toxicities of therapy, as men will likely live with these side effects for many years.

The standard therapy for metastatic and recurrent Pca is ADT, a potentially toxic therapy. It is well established that ADT can cause significant morbidity, including fatigue, anemia, osteopenia/osteoporosis and decrease in muscle mass, occurring as early as 1-3 months after ADT initiation.⁵⁻⁸ Patients on ADT for one year have a lower relative muscle mass, reduced upper limb strength, and worse self-reported physical function than those not on ADT.⁹ Increased prevalence of fractures in Pca patients on ADT has also been reported, with a positive correlation between number of LHRH agonist doses and fracture risk.¹⁰ Because older men are a "compromised host" who are already experiencing increased comorbidities, limited life expectancy and loss of muscle mass resulting in impaired muscle function associated with aging, they are particularly vulnerable to the potential side effects of therapy. In fact, several of the known toxicities of ADT, including sarcopenia, weakness, mobility problems, and fatigue, are part of the classic components of frailty - a geriatrics syndrome which imparts significant risk for adverse outcomes including falls, disability, hospitalization, and death.^{5,11-14} We have hypothesized that ADT may, indeed, *induce* frailty in a subset of older men with Pca (Figure 1).^{15,16} Despite the known toxicities and lack of survival benefit in many cases, the *use of ADT has increased by 27%* in less than a decade.¹⁷

It is well established that older patients experience age-related loss of muscle mass and function (sarcopenia), presumably due to an imbalance of protein synthesis versus protein breakdown. It addition, studies have shown that men who start on ADT experience increased muscle protein breakdown and decreased synthesis. 20 β -hydroxy- β -methylbutyrate (HMB), a leucine metabolite, has been shown to slow protein breakdown. When HMB is given with arginine and lysine (which support protein synthesis) in randomized trials, researchers have shown that elderly men and women who receive this nutritional supplementation experience improvement in fat-free mass, strength, functionality and protein synthesis when compared with controls. In addition, patients with advanced cancer who experienced weight loss of at least 5% have also been shown to benefit from HMB, with supplementation resulting in a significant increase of fat-free mass when compared to controls. Thus, it seems reasonable that older men with Pca starting on ADT who experience lean muscle loss as a result of aging and ADT, may achieve some benefit from supplementation with HMB as well.

Strength can be defined as the maximal voluntary force generating capacity of a muscle or muscle group (i.e., MVC). Muscle strength is directly related to muscle mass, and in turn, to muscle contractile or fat-free cross-sectional area (CSA). Muscle CSA in older adults can be measured accurately and non-invasively by magnetic resonance imaging (MRI) techniques and much of what we know about sarcopenia comes from such studies. Specific strength is the ratio of MVC/CSA. A loss of muscle mass, such as from sarcopenia, can lead to weakness without a change in specific strength. A decrease in specific strength would be indicative of central activation failure or a change in the intrinsic ability of the muscle to contract (i.e., altered intramuscular proteins).

Muscle fatigue can be described as a decrease in the force generating capacity of muscle or as a decreased time to task failure or endurance time. Muscle fatigue has been extensively investigated in older adults and in PCa survivors undergoing radiotherapy using standard electrophysiological techniques. Muscle oxidative capacity, an index of muscle fatiguability, can be indicated by the 31P-MRS during conscious exercise in humans and has been used to successfully study muscle fatigue in chronic disease. Research

Muscle biopsies can be used to better understand the pathophysiology behind muscle loss. There are two types of muscle fibers: fast and slow. Slow muscle fibers are important for postural standing, while fast muscle fibers are important for quick movements such as catching oneself while tripping. Both are important in older patients prone to falls. Muscle biopsies have been done in healthy subjects; the procedure is minimally invasive and well-tolerated. Muscle biopsies have been done in healthy subjects.

We propose to study to use of HMB plus amino acids in older men with Pca starting ADT. We hypothesize that the use of this nutritional supplementation will decrease the loss of muscle mass and strength that occurs when men start ADT. Use of HMB in men with prostate cancer has not been reported, thus this is a completely novel study. The strength of this project lies in the multidisciplinary approach to evaluation of muscle loss and strength in this patient population. We plan to use geriatric functional assessments, MRI measurements and pathologic evaluation of muscle. We have incorporated a very diverse team including medical oncology, geriatrics, radiology, pathology and exercise physiology, with each member of the team adding their extensive expertise in their given area. For this reason, we feel that this is a very strong proposal which will fundamentally address a promising approach to this important clinical problem.

Preliminary data:

Abnormal physical performance and frailty in older men on ADT ([name]). In a cross-sectional study of 50 older men (age ≥70) with Pca on long-standing ADT, we found that these men are markedly disabled.³¹ 50% had abnormal scores on the Vulnerable Elders Score, a geriatric screening tool that identifies patients at risk for functional decline. 24% had impairments in Activities of Daily Living (ADLs); 42% had impairments in Instrumental Activities of Daily Living (IADLs); 50% had abnormal physical performance measures, and 22% reported a fall in the last 3 months. All of these exceed percentages for age- and gender-matched populations.

Table 1. Case-control study comparing frailty/disability for older men on ADT for 6+ months vs. controls off ADT.					
	Mean ± SD or %	p-value			
	ADT (N = 63)	Controls (N = 71)			
Age	72.1± 7.0	70.5 ± 6.3	0.21		
Body Mass Index					
Underweight (< 18)	0.0	0.0	0.04		
Normal (18.5-25)	13.5	20.6			
Overweight (25-30)	40.4	58.8			
Obese I & II (30-40)	40.4	19.1			

3. HYPOTHESIS AND OBJECTIVES

Use of HMB and/or amino acid supplementation in older men with PCa starting on ADT has not been reported. We will prospectively: 1) measure the change in body composition, strength, physical performance, and falls in older men with PCa starting on ADT, comparing those who receive HMB + AG versus those who do not, 2) evaluate the use of MRI and muscle biopsy to identify changes in muscle composition and muscle fatiguability that are known to occur in this patient population. We will test the hypothesis that HMB + AG can reduce the adverse change in body composition and strength/muscle fatiguability that occur when older men with Pca are started on ADT. With data obtained in this study, a larger randomized study will be designed to

compare interventions aimed at minimizing the adverse affects that occur with ADT initiation.

Objectives:

- 1. Prospectively measure the change in body composition, strength, physical performance measures, and falls in older men with PCa starting on ADT, comparing those who receive HMB + AG versus those who do not.
 - Hypothesis: Men who are randomized to receive HMB + AG will experience less lean body mass loss, less decrease in strength, less decline in physical performance, and fewer falls than those who do not receive HMB + AG.
- 2. Prospectively measure the fatiguability and muscle size using MRI/Phosphorus MRI spectroscopy (³¹P-MRS) in older men with PCa starting on ADT, comparing those who receive HMB + AG versus those who do not.
 - Hypothesis: Men who are randomized to receive HMB + AG will experience less muscle fatigue and less loss of muscle cross-sectional area than those who do not receive HMB + AG.
- 3. Prospectively analyze muscle fiber cross sectional area and fiber type using muscle biopsy in a subset of men with PCa starting ADT, comparing those who receive HMB + AG versus those who do not. Hypothesis: Men who are randomized to receive HMB+ AG will experience less loss of cross-sectional area and less loss of fast type II fibers than those who do not receive HMB + AG.

4. SELECTION OF PATIENTS

Prostate cancer patients under the care of an MCW Cancer Center physician will be eligible to participate.

Inclusion criteria:

- 1) Histologically confirmed adenocarcinoma of the prostate
- 2) Age 60 years or older
- 3) Patients with asymptomatic or minimally symptomatic PCa for which they are about to start androgen deprivation therapy (ADT) per provider recommendation
 - Asymptomatic or minimally symptomatic (as judged by treating physician) metastases allowed
 - Men receiving ADT for localized prostate cancer are allowed
- 4) Patient able to give informed consent.

Exclusion criteria:

- 1) Patient already on ADT
- 2) Patients who are visiting clinic for a second opinion only
- 3) Patients with a diagnosis of dementia
- 4) Patients with a diagnosis of a neuromuscular disorder (i.e. multiple sclerosis)

5. STUDY DESIGN AND STATISTICAL CONSIDERATIONS

Objective 1: Prospectively measure the change in body composition, strength, physical performance measures, and falls in older men with PCa starting on ADT, comparing those who receive HMB + AG versus those who do not.

Rationale: Older men with prostate cancer who start on ADT experience clinically significant muscle loss and weakness as a result of treatment, likely contributing to increase risk of falls and fractures and decreased quality of life. Treatments are needed which counteract the loss of muscle mass and strength caused by ADT. HMB + AG, which decreases protein/muscle breakdown, has been shown to increase lean muscle mass and strength in elderly men and women. It seems plausible that HMB + AG could counteract the muscle loss and weakness that men experience as a result of ADT; effectiveness of HMB + AG in men with prostate cancer starting ADT has not been studied.

Experimental Design: We will conduct a prospective cohort pilot study of men age 60 and older with Pca who are about to start ADT. All men will be followed prospectively for 3 months from time of initiation of ADT. Men will be randomized to receive HMB + AG versus no supplement (Figure 2). Assessments will be performed at baseline (before or within 2 weeks of starting ADT) and 3 months (Table 2). Adherence to HMB will be assessed by patient diaries. Functional assessments and basic strength measurements will be performed at baseline and 3 months. These will include the Short Physical Performance Battery (SPPB), a validated measure which evaluates balance, gait, strength, and endurance and has been shown to predictive of morbidity and mortality at 4 years. Hand dynamometer (grip strength, predictive of morbidity and mortality on older patients) and 3 month history of falls will also be assessed. Physical activity will be measured with tri-axial accelerometers (Actigraph, Pensacola FL) that persons will wear on a belt around the waist for 7-days. This has been used previously in men with prostate cancer. Body composition will be measured with Dual-emission X-ray absorptiometry (DXA) scan at baseline and 3 months. Muscle strength will be measured with non-magnetic force transducers and composition will be measured with MRI at baseline and 3 months (SA2). Muscle biopsies will be done on a subset of patients who agree to the procedure (SA3).

Setting: The patients will be recruited from Oncology and Urology clinics at Froedtert Hospital. PCa patients in the clinics who consent to participate in this study will do physical performance testing at each assessment. A trained research assistant (RA) will administer testing and enter data into a secure database. Serious adverse events and study progress for this investigator initiated trial will be monitored by [name] per NCI CCSG guidelines. Recruitment: Based on the number of patients currently seen in these clinics, approximately 2-3 patients will be seen a week who are eligible for this study. A total of 80 patients (40 in each arm) will be enrolled in this pilot study.

[figure not shown]

Table 2: Measures performed over time per group						
	Baseline			3 months		
	SPPB			SPPB		
	HD	MRI	Biopsy	HD	MRI	Biopsy
	falls		. ,	falls		
Control	Χ	X*	X*	Χ	X*	X*
HMB	Χ	X*	X*	Χ	X*	X*

SPPB: Short Physical Performance Battery; HD: hand dynamometer:

* MRI and Biopsy to be done on subset of sample

Data Analysis:

Study design: The trial will be conducted in two phases, with 40 patients recruited for both phases. After the first 40 patients have been evaluated, a two-sample one-sided t-test comparing the mean lean body mass loss will be conducted. If the one-sided p-value is equal or less than 0.0088, the trial will be stopped for efficacy. If the p-value exceeds 0.3, the trial will be stopped for futility. In all other cases the trial will proceed to the next phase. At the end of the second phase a two-sample one-sided t-test comparing the mean lean body mass loss in the two groups will be conducted at a 5% significance level. Randomization: Randomization will be stratified by exercise status to ensure almost equal representation of both strata in both treatment groups. A block-size of 8 will be used, that is among each 8 consecutive patients exactly 4 will receive each treatment. Due to the presence of strata this blocking will not ensure exactly equal group size, however compared to unblocked randomization it will keep the group-size difference lower. Sample size considerations: The study was powered to detect a smaller lean body mass loss by 0.8 kg in the treated group using a one-sided twosample t-test at a 5% significance level. This effect size corresponds to approximately 50% of the expected lean body mass loss in the control group, and is similar to the effect achieved by an exercise intervention.³⁸ Based on literature review the standard deviation of within-person lean body mass change was assumed to be 1.4kg.^{38,39} The following table shows the power of the study and the probability of early stopping for efficacy/futility with the planned total sample size of 40 subjects per group and one interim analysis after 20 patients. The values are based on 10,000 simulation runs.

Difference in lean body	Probability of early stopping	Probability of early stopping	Overall
mass loss, kg	for efficacy	for futility	power
0	0.9%	70.3%	4.7%
0.4	6.5%	35.4%	33.7%
0.8	26.4%	10%	78.0%
1.2	59.5%	1.5%	97.5%
1.6	86.8%	0.1%	99.8%

Statistical analysis plan: As described in the study design, the primary outcome of within-person lean body mass change will be analyzed using a one-sided two-sample t-test. This test will be conducted at a 0.88% significance level after 20 patients have been evaluated in both arms, and, if the study proceeds to the end, at a 5% significance level after 40 patients have been evaluated in both arms. The secondary outcomes will be evaluated using a t-test or Wilcoxon rank-sum test as appropriate.

Anticipated Results/Interpretation: We anticipate that body composition will be better preserved in the supplemented group after initiation of ADT. In addition, we expect less functional limitations to mobility in the supplemented group as indicated by greater physical activity as measured by accelerometry. Further we expect physical activity to be positively related to muscle strength and endurance.

Objective 2: Prospectively measure the fatiguability and muscle size using MRI/Phosphorus MRI spectroscopy (³¹P-MRS) in older men with PCa starting on ADT, comparing those who receive HMB + AG versus those who do not.

Rationale: Fatigue is highly prevalent in men with PCa undergoing ADT and can affect QOL. Muscle fatigue could be due decreased oxidative capacity as a primary or secondary effect of the cancer or its treatment. Fatigue could also result from muscle weakness or loss of strength. The later could occur when a smaller amount of muscle has to accomplish the same amount of work as that of a larger amount. 31P- MRS is a non invasive *in vivo* technique which can be used to study phosphorus energy metabolites in conscious humans during exercise. As such, it can help to delineate the causes of muscle fatigue in PCa with ADT. We expect both to play a role. HMB + AG has been shown to increase muscle strength in older patients. It stands to reason that muscle strength and fatiguability would improve in older men with prostate cancer on ADT who receive HMB + AG.

Experimental Design: A subset of consenting patients (estimated 20 per group) will be assessed at time increments as outlined above. Cross sectional area of quadriceps muscle will be assessed using MRI. Muscle fatiguability will be measured as time to task failure (i.e. endurance and PCr recovery) using 31P-MRS at baseline and 3 months.

Data Anlaysis: Exploratory MRI studies will be conducted on the first 40 consenting patients. This sample size will provide an 80% power to detect large effects with effect size of 0.9 or above at a two-sided 5% significance level.

Anticipated Results/Interpretation: We expect lean cross sectional area and therefore strength to be preserved or enhance in the HMG+AG group. We also expect endurance and muscle oxidative capacity to be preserved or enhanced in the HMG+AG group.

Objective 3: Prospectively analyze muscle fiber cross sectional area and fiber type using muscle biopsy in a subset of men with PCa starting ADT, comparing those who receive HMB + AG versus those who do not.

Rationale: Studies in older patients indicate that HMB, when given with amino acids, helps to maintain protein synthesis and slow muscle breakdown. ADT is known to cause accelerated loss of lean muscle mass. HMB + AG, when given to men starting androgen deprivation therapy, may prevent loss of lean muscle mass. Biopsy of muscle will definitively show cross sectional area and fiber type (fast versus slow) in this patient population. A better understanding of changes in fiber type will clarify the pathophysiology behind ADT toxicity and the potential mechanism of action of HMB + AG.

Experimental Design: A subset of patients will undergo muscle biopsy (vastus lateralis) at baseline and 3 months. We will compare pre-ADT versus post-ADT muscle biopsy for fiber type composition and fiber type cross sectional area. Muscle fiber type histochemical staining will be done as follows: 1) Biopsies will be quick frozen in isopentane cooled with liquid nitrogen, 2) Store frozen pre sample at -80C until get individual's post sample, 3) Cut 10 micron cross sections of pre and post and collect sections on same slide; process together in same incubation medium to prevent variation in day to day composition of the incubation conditions, 4) Incubate slides for histochemical myofibrillar ATPase activity using acid-preincubation and alkaline-preincubation to accentuate fast and slow fiber subtypes, 40 5) Based on muscle fiber staining intensities, quantified with MetaMorph computerized optical density readings, segregate fibers into fast and slow fiber types and determine the percentages of each type. For each fiber, measure its cross sectional area using MetaMorph digitizing planimetry. A separate consent form will be provided to consent for this procedure. We will compare those who receive HMB + AG to those who do not.

Data Analysis: Exploratory muscle biopsies will be conducted on the first 10 consenting patients. This sample size will provide an 80% power to detect large effects with effect size of 0.9 or above at a two-sided 5% significance level.

Anticipated Results/Interpretation: The percentage of fast fibers will decrease post ADT. Slow fibers will transform from slow to fast (shift in gene expression from slow myosin to fast myosin). The cross sectional areas of fast and slow fibers will decrease post ADT. ADT causes decreased synthesis of contractile proteins so muscle fibers atrophy. The post ADT shift in slow to fast fibers and fiber atrophy will cause the individual to

exhibit greater muscle fatigue and weakness. The fast fibers are more fatigable than slow fibers. Slow fibers are normally utilized to maintain posture, against gravity. They can contract for long periods without fatiguing. Fast fibers are fatigable so the person is likely to have difficulty maintaining posture. The reduced cross sectional areas of both fiber types represent a decrease in contractile proteins and less force output of the muscle. The individual is more likely to fall. HMB + AG treatment will prevent the post ADT shift from slow to fast fiber transformation and prevent muscle fiber atrophy. HMB individuals will have less fatiguability, stronger and less likely to fall.

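### The fixed 3-month falls history need not match the interval between visits, so a fall just before a late baseline can be counted at both visits

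*Combined protocol and SAP*

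**What the plan says.** The Objective 1 hypothesis in Section 3 includes a between-arm claim on falls: the supplemented men are expected to have "fewer falls than those who do not receive HMB + AG". Falls are therefore a named secondary outcome.

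Section 5 (Objective 1, Experimental Design) sets three timing rules:

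- **Recall period:** "3 month history of falls will also be assessed".
- **Visits:** "Assessments will be performed at baseline (before or within 2 weeks of starting ADT) and 3 months (Table 2"). No earliest date is given for baseline and no window for the second visit. Table 2 lists falls under both visits.
- **Follow-up:** "All men will be followed prospectively for 3 months from time of initiation of ADT".

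Section 7 suggests a different clock. It ends adverse-event collection 30 days after study completion and equates that point with 4 months from enrollment, so completion comes about 3 months after enrollment.

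The Section 5 analysis plan tests secondary outcomes with a t-test or a Wilcoxon test. It makes no allowance for time at risk.

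**The concern.** A look-back of fixed length, counted from the visit date, covers exactly the time between the two visits only if they are exactly 3 months apart. The plan does not require that. If the visits are closer together, the follow-up history reaches back past baseline and shares days with the baseline history. If they are further apart, some days are in neither.

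A fall reported at both visits cancels in a change score. If randomization follows baseline, a pre-baseline fall cannot have been affected by allocation, so counting it as an outcome pulls the arms together. Days in neither history lose events if they belong to the treatment period. The planned tests repair none of this. Section 3 also says the data will be used to design a larger randomized study, so a fall rate with a clear time at risk has value beyond the test itself.

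**Working it through.** The plan states no power or event rate for falls, so there is no figure of its own to reproduce. The check is window arithmetic followed by an illustration.

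**Inputs from the documents.** Look-back of 3 months, taken as 91 days; second visit 3 months after ADT start, so day 91 (Section 5 clock); latest baseline on ADT day 14; 40 men per arm (Section 5). Fall frequencies are 22% in 3 months (Section 2, Preliminary data) and 14.3% in 6 months, or about 7.15% in 3 (Table 1, ADT group).

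**Windows.** Let b be the baseline day counted from ADT start. The follow-up look-back opens on day 91 − 91 = 0, the day ADT starts, and the visits are 91 − b days apart. If b > 0, b look-back days precede baseline. If b < 0, |b| days after baseline are in neither history.

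| Baseline day b | Days between visits | Mismatch |
|---|---|---|
| +14 | 77 | 14/91 = 15.4% of look-back precedes baseline |
| +7 | 84 | 7/91 = 7.7% of look-back precedes baseline |
| 0 | 91 | none |
| −14 | 105 | 14/105 = 13.3% of interval uncovered |
| −28 | 119 | 28/119 = 23.5% of interval uncovered |

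The +14 row is the limit the plan allows. The two negative rows are assumed lead times, because the plan gives none.

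**Fallers per arm, overlap only, with every man at the maximum:**

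- At 22%: 40 × 0.22 = 8.8 men; 8.8 × 14/91 = 1.4.
- At 7.15%: 40 × 0.0715 = 2.9 men; 2.9 × 14/91 = 0.4.

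If every baseline instead fell evenly over ADT days 0 to 14 (an assumption), the mean overlap is 7 days, giving 8.8 × 7/91 = 0.7 and 2.9 × 7/91 = 0.2. Men with baseline on or before ADT start contribute no overlap.

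**Effect on the comparison.** Assume a constant fall hazard λ, a hazard ratio of 0.5, a 14-day overlap in every man, and no treatment effect in those 14 days. At 22%, λ = −ln(0.78)/91 = 0.00273 per day.

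- Post-baseline days only: control 1 − exp(−77λ) = 0.190; treated 1 − exp(−0.5 × 77λ) = 0.100; risk ratio 0.53.
- Fixed look-back: control 0.220; treated 1 − exp(−(0.5 × 77 + 14)λ) = 0.134; risk ratio 0.61.

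Two-sided power to compare the proportions of fallers with 40 per arm goes from about 20% to 17%. At the lower rate the risk ratio goes from 0.51 to 0.59 and power from about 9% to 8%.

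**The case against.** **The second-visit anchor is inferred.** Section 5 schedules the assessment only at 3 months. On the Section 7 clock, if enrollment and baseline coincide, the windows match and nothing overlaps. This stands as a reason to reconcile the two sections. It does not remove the point, because Section 5 expressly starts follow-up at ADT initiation. Enrollment and a late baseline also need not coincide: "Patient already on ADT" is an exclusion, so a baseline on ADT days 1 to 14 comes after eligibility was met.

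**The uncovered days may not be follow-up at all.** A 3-month look-back from ADT month 3 covers exactly the follow-up period Section 5 declares. A reader might infer that falls after randomization are being missed. The documents do not support that: the readable text does not date randomization or the start of the supplement relative to baseline or ADT, and Figure 2 is not shown. Nor is there any basis for calling a particular lead time typical.

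**The effect is small.** This stands. Power for falls is very low with or without the mismatch, so it changes little about what the trial can conclude.

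**Equal 3-month windows make the two raw counts comparable.** This also stands, and it is a real cost of changing the question.

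**Conclusion.** The point holds as a minor design weakness. On the Section 5 clock, the plan as written allows up to 14 of about 91 follow-up look-back days (15%) to precede baseline, with any fall in them counted at both visits. Days between an early baseline and ADT start are in neither history; whether they are lost outcomes cannot be settled from the readable text. In the same way, the overlap days precede randomization only if randomization follows the baseline visit.

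The 15% is a per-man maximum. A reader might take 1.4 of about 9 fallers (or 0.4 of about 3) as the expected error per arm, but it is a ceiling that needs every man to have a day-14 baseline. Both fall rates come from men already on longer-term ADT, not men starting it. A reader might also infer a biased comparison. If baseline timing is balanced between arms, the expected result is mainly dilution and noise, not a shift in a known direction. The power figures rest on the assumed hazard ratio and constant hazard. The primary lean-mass test does not use the falls history.

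**What to change.** - Keep the 3-month history at baseline.
- At the second visit, ask both arms about falls since the baseline visit, with approximate dates, and record the days between visits.
- In the analysis plan, compare arms on post-baseline falls allowing for days at risk, for example falls per day at risk with the Wilcoxon test already planned.
- Reconcile the follow-up clocks in Sections 5 and 7, and state when randomization and supplementation start relative to baseline and ADT.

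**Cost.** One reworded question, one recorded interval and a sentence in the analysis plan; no added visit. Recall length will vary by some weeks between men. Raw baseline and follow-up counts will no longer cover equal periods, so any change must be expressed as a rate.

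### A single fixed block size of 8, printed in the protocol of a trial with a no-supplement control arm, could let someone who tracks the strata know up to about one allocation in five in advance.

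*Combined protocol and SAP*

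**What the plan says.** All of this is in section 5 of the combined protocol and SAP.

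- **Block rule** (Data Analysis, Randomization): "A block-size of 8 will be used, that is among each 8 consecutive patients exactly 4 will receive each treatment".
- **Stratification** (same paragraph): "Randomization will be stratified by exercise status to ensure almost equal representation of both strata in both treatment groups". The plan accepts that "Due to the presence of strata this blocking will not ensure exactly equal group size", which implies that the blocks run separately within each stratum.
- **Comparison** (Objective 1, Experimental Design): "Men will be randomized to receive HMB + AG versus no supplement". No placebo or blinding is described for this trial. The only mention of placebo, in section 6, concerns prior studies.
- **Setting and size** (Setting; Recruitment): "The patients will be recruited from Oncology and Urology clinics at Froedtert Hospital", and "A total of 80 patients (40 in each arm) will be enrolled in this pilot study".
- **Primary test** (Study design; Statistical analysis plan): a one-sided two-sample t-test on lean body mass change, with an interim look at 20 per arm.

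The documents do not say who holds the list, how allocation is concealed, or when an assignment is released relative to consent and baseline measurement.

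**The concern.** When the block length is fixed and known, and past assignments can be seen, the end of each block is determined: once one arm has its four patients, the rest of the block must go to the other. Here the length is in the protocol, and assignments are hard to hide because one arm takes a supplement and the other takes nothing.

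Foreknowledge acts before enrolment, on who is offered the trial and when. An objective endpoint such as DXA does not protect against that, because the arms may already differ in who entered them. The primary analysis is an unadjusted one-sided test, so a selection effect favouring the supplement would raise the false-positive rate directly. The trial is also meant to inform a larger randomized study, so a distorted result would carry forward.

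**Working it through.** **1. The plan's own figures reproduce.** Inputs from the sample-size paragraph: difference 0.8 kg, SD 1.4 kg, 40 per arm, interim at 20 per arm, stop for efficacy if p ≤ 0.0088, stop for futility if p > 0.3, final one-sided 5%. Simulating this design (100,000 runs per row) gives 78.3% power at 0.8 kg (stated 78.0%) and 4.8% type I error at 0 kg (stated 4.7%). The power table is sound. The plan gives no figure for predictability.

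**2. Share of allocations that can be certain, fixed block of 8.** A 4:4 block has C(8,4) = 70 equally likely orderings. An allocation is forced when one arm has already used its four places.

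| Position | Orderings in which it is forced | Probability |
|---|---|---|
| 1 to 4 | 0 of 70 | 0 |
| 5 | 2 of 70 | 2.9% |
| 6 | 10 of 70 | 14.3% |
| 7 | 30 of 70 | 42.9% |
| 8 | 70 of 70 | 100% |

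The expected number forced per block is (2 + 10 + 30 + 70)/70 = 112/70 = 1.6, and 1.6/8 = 20.0%. The closed form for a block of 2m agrees: 2m/(m+1) = 8/5 = 1.6 for m = 4.

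**3. Incomplete last blocks.** Taking two strata and every split of 80 patients between them, the forced share is 18.0% to 20.0%, or 14.4 to 16 patients. If the trial stops at 40 patients it is 16% to 20%.

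**4. Best guess.** Always guessing the arm that is behind in the current block is right 66.6% of the time, against 50% with no information.

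**5. With varied block sizes.** This was simulated for 40 patients in a stratum and a guesser who knows the set of sizes, but not which is in use, and updates on every past assignment.

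| Block sizes | Known with certainty | Best-guess rate |
|---|---|---|
| 8 only | 20.0% | 66.6% |
| 4, 8 | 7.0% | 67.8% |
| 4, 6, 8 | 2.2% | 67.7% |
| 6, 8, 10 | 1.8% | 65.9% |

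Varying the sizes removes nearly all the certainty and hardly touches informed guessing.

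**6. What a bias would do (illustration; the biases are assumed).** Adding a constant to the treated-minus-control difference under the null and running the two-stage rule:

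| Assumed bias | One-sided type I error |
|---|---|
| 0 kg | about 4.8% |
| 0.07 kg | about 7.3% |
| 0.14 kg | about 10.8% |

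Simulation error is a few tenths of a point at most. For scale, suppose selection acted only on the 20% of allocations that are certain, in both arms and in the favourable direction. A 0.14 kg bias then needs those men to differ by d, where 0.2 × 2 × d = 0.14. This gives d = 0.35 kg, or 0.35/1.4 = 0.25 SD.

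**The case against.** The case on the other side has several parts.

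- **The 20% is a ceiling.** It applies to someone who knows the block size, sees every assignment from both the Oncology and the Urology clinics, and keeps a count per exercise stratum. The documents do not say that recruiters see the sequence; the research assistant is mentioned only for testing and data entry. A reader might infer that recruiting staff will know one allocation in five. The text supports only that someone could. This part stands.
- **Varying the blocks does not reduce guessing.** The best-guess rate is 66.6% with fixed blocks of 8 and about 67.7% with 4/6/8. Bias from steering patients towards the arm that is behind would not fall. This stands too, and is why non-disclosure and late release matter as much as the block sizes.
- **The harm is hypothetical.** Nothing in the documents supports a bias of 0.07 or 0.14 kg. Because the outcome is within-person change, staff would have to predict three-month change in lean mass, not merely pick fitter men. A reader might infer that the planned type I error is already inflated. It is not: the planned figure reproduces at about 4.8%.
- **Blocks of 8 are conventional** in a single-hospital pilot of 80, and 8 is not a small block. True, but that does not justify fixing and printing the size when avoiding both costs so little. A concealment procedure may also exist elsewhere; none is described here.

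**Conclusion.** The point holds as an avoidable weakness in the randomization procedure. With the block size fixed, printed and applied in a trial that is open in effect, up to 20% of allocations could be known in advance for complete blocks, and 18% to 20% at 80 patients. This assumes two strata, a known block size and a running count in each stratum. Stratification does not lower the share for complete blocks, because stratum is known before randomization; it only means keeping two counts. Someone who sees only one clinic's patients would know less.

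That the trial is open-label is inferred from the no-supplement arm and the absence of any described blinding; the documents do not use the term. They do not show that selection will occur, and the type I error figures above illustrate an assumed bias only. The planned test, sample size and power table are unaffected. This is a cheap improvement worth making, not a flaw that invalidates the design.

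**What to change.** In the Randomization paragraph of section 5, replace the fixed block of 8 with wording such as: *Within each exercise stratum, assignments will be generated in randomly permuted blocks of randomly varied size. The sizes are recorded in a document held only by the statistician. Each assignment is released only after consent has been given and the baseline DXA has been completed.* Sizes of 4, 6 and 8 would serve, but should not appear in the protocol.

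Allocations known with certainty fall from 20% to about 2% if the set of sizes leaks, and lower if it does not. All three parts are needed, because the best-guess rate stays near 67%.

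The cost is a new randomization list, the revised wording, and the discipline of holding each assignment until the baseline scan is done. Arm balance may be very slightly worse or better: in a stratum of 40, fixed blocks of 8 end exactly balanced, while mixed 4/6/8 leaves a mean absolute difference of about 0.56 patients; in a stratum of 37 the figures are about 1.27 (fixed) and 1.08 (mixed). Sample size and power do not change.
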